## 2. Selection of Patients

Each of the criteria in the checklist that follows must be met, along with the eligibility in the MATCH Master Protocol, in order for a patient to be considered eligible for this study. Use the checklist to confirm a patient's eligibility. For each patient, this checklist must be photocopied, completed and maintained in the patient's chart.

**In calculating days of tests and measurements, the day a test or measurement is done is considered Day 0. Therefore, if a test is done on a Monday, the Monday four weeks later would be considered Day 28.**

ECOG-ACRIN Patient No. \_\_\_\_\_

Patient's Initials (L, F, M) \_\_\_\_\_

Physician Signature and Date \_\_\_\_\_

**NOTE:** Policy does not allow for the issuance of waivers to any protocol specified criteria ([http://ctep.cancer.gov/protocolDevelopment/policies\\_deviations.htm](http://ctep.cancer.gov/protocolDevelopment/policies_deviations.htm)). Therefore, all eligibility criteria listed in Section 2 must be met, without exception. The registration of individuals who do not meet all criteria listed in Section 2 can result in the participant being censored from the analysis of the study, and the citation of a major protocol violation during an audit. All questions regarding clarification of eligibility criteria must be directed to the Group's Executive Officer ([[contact]](mailto:[contact])) or the Group's Regulatory Officer ([[contact]](mailto:[contact])).

**NOTE:** Institutions may use the eligibility checklist as source documentation if it has been reviewed, signed, and dated prior to registration/randomization by the treating physician.

**NOTE:** All patients must have signed the relevant treatment consent form

### 2.1 Eligibility Criteria

- \_\_\_\_\_ 2.1.1 Patients must fulfill all eligibility criteria outlined in Section 3.1 of MATCH Master Protocol (excluding Section 3.1.6) at the time of registration to treatment step (Step 1, 3, 5, 7).
- \_\_\_\_\_ 2.1.2 Patients must have an AKT mutation as determined via the MATCH Master Protocol and described in [Appendix II](#). See [Appendix II](#) for information on the AKT mutation and corresponding Levels of Evidence.
- \_\_\_\_\_ 2.1.3 Patients with breast cancer are excluded.
- \_\_\_\_\_ 2.1.4 Patients with castration-resistant prostate cancer should maintain castrate levels of testosterone (i.e., with GnRH agonists or through surgical castration). Patients are allowed to continue abiraterone acetate / prednisone with Ipatasertib if the patient just progressed on abiraterone acetate / prednisone.
- \_\_\_\_\_ 2.1.5 Patients must not have known hypersensitivity to Ipatasertib or compounds of similar chemical or biologic composition.
- \_\_\_\_\_ 2.1.6 Patients with known KRAS, NRAS, HRAS, or BRAF mutations are not eligible for this protocol, as these mutations may lead to limited response due to resistance.

Rev. Add25

\_\_\_\_\_ 2.1.7 Patients with diabetes or risk for hyperglycemia are eligible. Patients with diabetes mellitus should be on a stable dose of oral hypoglycemic agents for  $\geq$  4 weeks and appropriate diet. Patients with diabetes mellitus may enter the study unless any of the following exclusion criteria are fulfilled:

- Baseline fasting glucose value of  $>8.9$  mmol/L or 160 mg/dL (fasting is defined as no calorific intake for at least 8 hours)
- Patients not on a stable dose of oral hypoglycemic medication for  $\geq$  4 weeks and appropriate diet
- Insulin required for routine diabetic management and control
- More than two oral hypoglycemic medications required for routine diabetic management and control
- Hemoglobin A1C  $\geq 7.5\%$

\_\_\_\_\_ 2.1.8 Prior PI3K and mTOR inhibitors are allowed, including in the metastatic setting. Prior AKT inhibitors are excluded (See [Appendix IV](#)).

\_\_\_\_\_ 2.1.9 Patients with a history of inflammatory bowel diseases (Crohn's disease and ulcerative colitis) or active diverticulitis are not eligible.

\_\_\_\_\_ 2.1.10 Patients may not have received strong inhibitors or potent inducers or substrates of CYP3A4/5 within 2 weeks before the first dose of study treatment (3 weeks for St John's Wort). See Section [5.1.8](#) and [Appendix III](#).

\_\_\_\_\_ 2.1.11 In addition to the patient contraception requirements outlined in EAY131 MATCH Master Protocol, male patients must also refrain from donating sperm for the duration of study participation, and for 4 months after completion of study.

---

Physician Signature

Date

**OPTIONAL:** This signature line is provided for use by institutions wishing to use the eligibility checklist as source documentation.

### 3. Ipatasertib Treatment Plan

#### 3.1 Administration Schedule

Patients will be instructed to take Ipatasertib 400 mg orally once daily continuously for each 28 day cycle, until tumor progression or unless patient experiences unacceptable toxicities. Cycles are defined in 28-day periods to facilitate scheduling of visits and assessments.

**NOTE:** Ipatasertib can be taken with or without food.

If a dose is missed or omitted (not taken within 8 hours after the scheduled dosing time), the patient should resume dosing with the next scheduled dose the following day. Missed, omitted, or vomited doses will not be made up. In the event that a patient vomits later than 30 minutes after Ipatasertib dosing, the patient must not retake new capsule(s)/tablet(s), but continue to take the next day. If a patient needs to take the dose earlier for whatever reason, the patient can take the dose up to 8 hours earlier than the scheduled dose time. The patient should make every reasonable effort to take the Ipatasertib capsule(s) / tablets(s) on time.

Rev. Add25

#### Hormone Therapy (Breast Cancer and/or Prostate Cancer)

If the patient has HR positive/HER2 negative unresectable breast cancer, (s)he is allowed to continue fulvestrant or an aromatase inhibitor (anastrazole, letrozole, exemestane) with Ipatasertib if (s)he most recently progressed on this anti-estrogen therapy. For instance, if the last treatment was fulvestrant, the patient is allowed to continue the fulvestrant in combination with Ipatasertib. If the patient previously was receiving GnRH agonist (such as leuprolide or goserelin), this should continue as previously administered.

SERMs, such as tamoxifen or toremifene, are not allowed.

If the patient has metastatic castration resistant prostate cancer, he is allowed to continue abiraterone if he just progressed on this agent. GnRH agonists (such as leuprolide or goserelin) are allowed. Prednisone/prednisolone is allowed along with this combination – up to 10 mg po daily (5 mg po bid is allowed).

The patient should continue on the same dose and schedule of the prior hormone therapy as was previously taken. Hormone therapy administration is per FDA-approved package labeling.

#### Diarrhea Prophylaxis

In this study all patients should receive loperamide (2 mg oral twice a day or 4 mg once a day) as prophylaxis for diarrhea in the first cycle if allowed by local guidance. Investigators are encouraged to continue this dosing for the remainder of the study, and the prophylaxis dose may be adjusted as necessary, using their discretion based on clinical judgment and per local guidance.

#### 3.2 Adverse Event Reporting Requirements

The Adverse Event Reporting Requirements for all EAY131 subprotocols are outlined in the MATCH MASTER protocol. Please refer to those guidelines when determining if an event qualifies as a Serious Adverse Event (SAE) and requires expedited reporting via CTEP's Adverse Event Reporting System (CTEP-AERS).

In addition, the following section outlines agent specific requirements and must be followed to ensure all reporting requirements are met.

3.2.1 Additional instructions, requirements and exceptions for protocol EAY131 – Subprotocol Z1K

**Additional Instructions**

For instructions on how to specifically report events that result in persistent or significant disability/incapacity, congenital anomaly, or birth defect events via CTEP-AERS, please contact the AEMD Help Desk at [[contact]](mailto:[contact]) or [contact]. This will need to be discussed on a case-by-case basis.

**EAY131 – Subprotocol Z1K specific expedited reporting requirements:**

- **Pregnancies:** Pregnancies and suspected pregnancies (including a positive or inconclusive pregnancy test, regardless of age or disease state) occurring while the female patient is on Ipatasertib, or within 28 days of the female patient's last dose of Ipatasertib, are considered immediately reportable events. The pregnancy, suspected pregnancy, or positive/ inconclusive pregnancy test must be reported via CTEP-AERS within 24 hours of the Investigator's knowledge. Please refer to Appendix VIII in MATCH Master Protocol for detailed instructions on how to report the occurrence of a pregnancy as well as the outcome of all pregnancies.

**EAY131 – Subprotocol Z1K specific expedited reporting exceptions:**

For Subprotocol Z1K, the adverse events listed below **do not** require expedited reporting via CTEP-AERS:

1. If an AE meets the reporting requirements of the protocol, and it is listed on the SPEER, it should **ONLY** be reported via CTEP-AERS if the grade being reported exceeds the grade listed in the parentheses next to the event.

3.2.2 Second Primary Cancer Reporting Requirements

All cases of second primary cancers, including acute myeloid leukemia (AML) and myelodysplastic syndrome (MDS), that occur following treatment on NCI-sponsored trials must be reported to ECOG-ACRIN using Medidata Rave

- **A second malignancy is a cancer that is UNRELATED to any prior anti-cancer treatment (including the treatment on this protocol). Second malignancies require ONLY routine reporting as follows:**
  1. Complete a Second Primary Form in Medidata Rave within 14 days.

2. Upload a copy of the pathology report to ECOG-ACRIN via Medidata Rave confirming the diagnosis.
3. If the patient has been diagnosed with AML/MDS, upload a copy of the cytogenetics report (if available) to ECOG-ACRIN via Medidata Rave.

- **A secondary malignancy is a cancer CAUSED BY any prior anti-cancer treatment (including the treatment on this protocol). Secondary malignancies require both routine and expedited reporting as follows:**
  1. Complete a Second Primary Form in Medidata Rave within 14 days
  2. Report the diagnosis via CTEP-AERS at <http://ctep.cancer.gov>  
*Report under a.) leukemia secondary to oncology chemotherapy, b.) myelodysplastic syndrome, or c.) treatment related secondary malignancy*
  3. Upload a copy of the pathology report to ECOG-ACRIN via Medidata Rave and submit a copy to NCI/CTEP confirming the diagnosis.
  4. If the patient has been diagnosed with AML/MDS, upload a copy of the cytogenetics report (if available) to ECOG-ACRIN via Medidata Rave and submit a copy to NCI/CTEP.

**NOTE:** The Second Primary Form and the CTEP-AERS report should not be used to report recurrence or development of metastatic disease.

**NOTE:** If a patient has been enrolled in more than one NCI-sponsored study, the Second Primary Form must be submitted for the most recent trial. ECOG-ACRIN must be provided with a copy of the form and the associated pathology report and cytogenetics report (if available) even if ECOG-ACRIN was not the patient's most recent trial.

**NOTE:** Once data regarding survival and remission status are no longer required by the protocol, no follow-up data should be submitted via CTEP-AERS or by the Second Primary Form.

3.3 Comprehensive Adverse Events and Potential Risks list (CAEPR) for Ipatasertib (NSC 781451)

The Comprehensive Adverse Events and Potential Risks list (CAEPR) provides a single list of reported and/or potential adverse events (AE) associated with an agent using a uniform presentation of events by body system. In addition to the comprehensive list, a subset, the Specific Protocol Exceptions to Expedited Reporting (SPEER), appears in a separate column and is identified with bold and italicized text. This subset of AEs (SPEER) is a list of events that are protocol specific exceptions to expedited reporting to NCI (except as noted below). Refer to the 'CTEP, NCI Guidelines: Adverse Event Reporting Requirements' [http://ctep.cancer.gov/protocolDevelopment/electronic\\_applications/docs/aeguidelines.pdf](http://ctep.cancer.gov/protocolDevelopment/electronic_applications/docs/aeguidelines.pdf) for further clarification. Frequency is provided based on 188 patients. Below is the CAEPR for Ipatasertib.

**NOTE:** Report AEs on the SPEER **ONLY IF** they exceed the grade noted in parentheses next to the AE in the SPEER. If this CAEPR is part of a combination protocol using multiple investigational agents and has an AE listed on different SPEERs, use the lower of the grades to determine if expedited reporting is required.

Version 2.0, September 16, 2021

Adverse Events with Possible Relationship to Ipatasertib (CTCAE 5.0 Term) [n= 188]			Specific Protocol Exceptions to Expedited Reporting (SPEER)
Likely (>20%)	Less Likely (<=20%)	Rare but Serious (<3%)	
BLOOD AND LYMPHATIC SYSTEM DISORDERS			
	Anemia		
GASTROINTESTINAL DISORDERS			
	Abdominal pain		Abdominal pain (Gr 2)
Diarrhea		Colitis	Diarrhea (Gr 2) Dyspepsia (Gr 2)
	Dyspepsia		
Nausea		Mucositis oral	Nausea (Gr 2) Vomiting (Gr 2)
	Vomiting		
HEPATOBILIARY DISORDERS			
		Hepatobiliary disorders - Other (hepatotoxicity)	
GENERAL DISORDERS AND ADMINISTRATION SITE CONDITIONS			
	Fatigue		Fatigue (Gr 2)
INVESTIGATIONS			
		Neutrophil count decreased	
		Platelet count decreased	
METABOLISM AND NUTRITION DISORDERS			
	Anorexia		Anorexia (Gr 2)

Adverse Events with Possible Relationship to Ipatasertib (CTCAE 5.0 Term) [n= 188]			Specific Protocol Exceptions to Expedited Reporting (SPEER)
Likely (>20%)	Less Likely (<=20%)	Rare but Serious (<3%)	
	Hyperglycemia		Hyperglycemia (Gr 2)
NERVOUS SYSTEM DISORDERS	Dysgeusia		Dysgeusia (Gr 2)
RESPIRATORY, THORACIC AND MEDIASTINAL DISORDERS		Pneumonitis	
SKIN AND SUBCUTANEOUS TISSUE DISORDERS		Erythema multiforme	
	Rash 		Rash (Gr 2)

This table will be updated as the toxicity profile of the agent is revised. Updates will be distributed to all Principal Investigators at the time of revision. The current version can be obtained by contacting [[contact]](mailto:[contact]). Your name, the name of the investigator, the protocol and the agent should be included in the e-mail.

Rash may include rash with or without pruritus, toxic skin eruption, and rash maculo-papular.

**Adverse events reported on Ipatasertib trials, but for which there is insufficient evidence to suggest that there was a reasonable possibility that Ipatasertib caused the adverse event:**

**CARDIAC DISORDERS** - Cardiac arrest

**GASTROINTESTINAL DISORDERS** - Abdominal distension; Gastroesophageal reflux disease

**INFECTIONS AND INFESTATIONS** - Skin infection

**INVESTIGATIONS** - Alanine aminotransferase increased; Aspartate aminotransferase increased; Cholesterol high; Investigations - Other (blood insulin increased); Investigations - Other (glucose urine present)

**METABOLISM AND NUTRITION DISORDERS** - Dehydration; Hypertriglyceridemia; Hyperlipidemia; Hypocalcemia; Hypokalemia; Hypomagnesemia; Hypophosphatemia

**MUSCULOSKELETAL AND CONNECTIVE TISSUE DISORDERS** - Arthralgia; Myalgia

**NERVOUS SYSTEM DISORDERS** - Dizziness; Headache; Paresthesia

**RENAL AND URINARY DISORDERS** - Acute kidney injury; Glucosuria

**RESPIRATORY, THORACIC AND MEDIASTINAL DISORDERS** - Dyspnea

**SKIN AND SUBCUTANEOUS TISSUE DISORDERS** - Dry skin; Skin and subcutaneous tissue disorders - Other (toxic skin eruption)

**VASCULAR DISORDERS** - Hypotension; Thromboembolic event

**NOTE:** Ipatasertib in combination with other agents could cause an exacerbation of any adverse event currently known to be caused by the other agent, or the combination may result in events never previously associated with either agent.

### 3.4 Dose Modifications

All toxicity grades below are described using the NCI Common Terminology Criteria for Adverse Events (CTCAE) version 5.0.

All appropriate treatment areas should have access to a copy of the CTCAE version 5.0. A copy of the CTCAE version 5.0 can be downloaded from the CTEP website

([http://ctep.cancer.gov/protocolDevelopment/electronic\\_applications/ctc.htm](http://ctep.cancer.gov/protocolDevelopment/electronic_applications/ctc.htm))

Patients will be monitored closely for toxicity and the dose of Ipatasertib may be adjusted as indicated in Table 1. Intra-patient dose reduction will be allowed depending on the type and severity of toxicity encountered.

If dose reduction is required, reduction is permanent and will not be brought back up to full dose. If doses are missed due to toxicity, these will not be made up.

**Table 1: Dose Levels for Ipatasertib**

Dose Level	Daily Dose/ Route	Dispensed As	Schedule
Starting dose level: 0	400 mg, PO	2 x 200-mg tablets	Once daily continuously for each 28 day cycle
-1	300 mg, PO	1 x 200 mg tablet 1 x 100 mg tablet	Once daily continuously for each 28 day cycle
-2	200 mg, PO	1 x 200-mg tablet	Once daily continuously for each 28 day cycle

Patients requiring more than 2 dose reductions due to treatment-toxicity will be removed from treatment. Patients requiring treatment to be held for >4 weeks will be taken off treatment.

**Table 2: Hematologic Toxicity**

Grade	Management/Next Dose for Ipatasertib
Grade 1	No change in dose.
Grade 2	No change in dose.
Grade 3	Hold* until ≤ Grade 2. Consider resuming at one dose level lower, per investigator discretion**.
Grade 4	Hold* until ≤ Grade 2. Resume at one dose level lower**.

\* Patients requiring Ipatasertib delay of >4 weeks will go off protocol therapy. Growth factor support is allowed, per investigator discretion. Transfuse PRBC as clinically indicated

\*\* Patients requiring > 2 dose reductions of Ipatasertib will go off protocol therapy.

**Table 3: Non-Hematologic Toxicities (except for diarrhea, nausea/vomiting, hyperglycemia, rash, pneumonitis, or hepatotoxicity)**

Grade	Management/Next Dose for Ipatasertib
Grade 1	No change in dose
Grade 2	Hold* until $\leq$ Grade 1. Recommend resume at same dose level, but per investigator discretion. If the toxicity is deemed probably or definitely related to Ipatasertib – and not reduced after the first occurrence - a dose reduction should be considered after a second recurrence, if still deemed probably or definitely related.
Grade 3	Hold* until $\leq$ Grade 1. Resume at one dose level lower**.
Grade 4	Hold* until $\leq$ Grade 1. Resume at one dose level lower or discontinue, per investigator discretion**.
* Patients requiring a delay of $>4$ weeks will be removed from protocol therapy.	
** Patients requiring $>$ two dose reductions will be removed from protocol therapy.	

**Table 4: Diarrhea Management**

#### Diarrhea Prophylaxis

In this study all patients should receive loperamide (2 mg oral twice a day or 4 mg once a day) as prophylaxis for diarrhea in the first cycle if allowed by local guidance. Investigators are encouraged to continue this dosing for the remainder of the study, and the prophylaxis dose may be adjusted as necessary, using their discretion based on clinical judgment and per local guidance.

Grade	Management/Next Dose for Ipatasertib
Grade 1	
 
No change in dose.
 
Manage with loperamide 4 mg initially, and then 2 mg every 4 hours or after every unformed stool until after 12-hour diarrhea-free interval (maximum daily total dose should not exceed 16 mg).
 
Dietary modifications such as avoiding any lactose-containing foods.
 
Hydration with 8–10 glasses of clear liquid such as broth and low-sugar electrolyte infused drinks per day.
 

Grade 2	
 
Interrupt Ipatasertib until diarrhea improves to Grade <math>\leq</math> 1.
 
Ipatasertib can be resumed at the same dose or one dose lower per investigator evaluation upon improvement to Grade <math>\leq</math> 1.
 
Manage with loperamide 4 mg initially, and then 2 mg every 4 hours or after every unformed stool until after 12-hour diarrhea-free interval (maximum daily total dose should not exceed 16 mg).
 
Dietary modifications such as avoiding any lactose-containing foods.
 
Hydration with 8–10 glasses of clear liquid such as broth and low-sugar electrolyte infused drinks per day.
 
For non-infectious diarrhea lasting more than 48 hours despite optimal loperamide treatment, manage with second-line anti-diarrheal agents, including, but not limited to Lomotil®, codeine, or octreotide, or as per institutional guidelines.
 

Grade	Management/Next Dose for Ipatasertib
	
 
Reduce Ipatasertib by one additional dose level for recurrent Grade 2 diarrhea.
 

Grade 3	
 
Treatment per Grade 2 management guidelines and supportive care.
 
Interrupt Ipatasertib until diarrhea improves to Grade <math>\leq</math> 1.
 
Ipatasertib should be reduced by one dose level when treatment is restarted.
 
For recurrent Grade 3 diarrhea, reduce Ipatasertib by one additional dose level or permanently discontinue Ipatasertib, per investigator discretion.
 

Grade 4	
 
Management as per Grade 3 guidelines.
 
Permanently discontinue Ipatasertib.
 

* Patients requiring a delay of <math>></math> 4 weeks will go off protocol therapy.
 
** Patients requiring <math>></math> two dose reductions will go off protocol therapy.
	

**Table 5: Nausea and/or Vomiting**

Dose reductions for nausea and/or vomiting should occur only if the symptoms persist despite a minimum of two treatments with adequate (combination) anti-emetic treatment(s), including ondansetron (or equivalent anti-emetic).

Grade	Management/Next Dose for Ipatasertib
Grade 1	
 
Provide maximum supportive care as needed.
 

Grade 2	
 
Provide maximum supportive care as needed.
 
Provide ondansetron (or equivalent anti-emetic medication) as needed.
 

Grade 3	
 
Hold* until <math>\leq</math> Grade 2.
 
Provide maximum supportive care as needed.
 
Provide ondansetron (or equivalent anti-emetic medication) as needed.
 
If Grade <math>\geq</math> 3 nausea or vomiting recurs, Ipatasertib should be reduced by one dose level when treatment is restarted.**
 

Grade 4	
 
Follow grade 3 recommendations
 

* Patients requiring a delay of <math>></math> 4 weeks will go off protocol therapy.
 
** Patients requiring <math>></math> two dose reductions will go off protocol therapy.
	

### Hyperglycemia

These guidelines are for random or fasting blood glucose results. These are general recommendations: due consideration should be given to baseline values and time since food when interpreting glucose results.

It is recommended that approaches to the management of Ipatasertib-induced hyperglycemia in diabetic patients include advice from the patient's endocrinologist where appropriate.

Home glucose measurements may be used to trigger contact between patient and the investigative site team and may lead to an unscheduled clinic visit to

assess glucose. Alternative thresholds may be selected as clinically indicated per investigator discretion or institutional guidance.

For Glucose Level 3 or 4 hyperglycemia, when insulin therapy is considered, an insulin infusion is recommended. Avoid use of long acting insulin, avoid large boluses of short acting insulin, and observe closely for rebound hypoglycemia.

The management recommendations described in Table 6 are based on those detailed by Busaidy et al for PI3K-AKT-mTOR pathway inhibitors.

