**Table 6: Hyperglycemia**

Glucose Level	Management/Next Dose for Ipatasertib
Level 1 (<8.9 mM; OR <160 mg/dL)	

• No change in dose.

• Patient should receive education on a diabetic diet.

• Consider home glucose monitoring, as per treating physician discretion.

Level 2 (≥ 8.9 mM and < 13.9 mM; OR > 160 mg/dL and < 250 mg/dL)	

• Hold* until ≤ Glucose Level 1.

• Initiate home glucose monitoring, as per treating physician discretion.

• Add or administer a higher dose of oral metformin.

• Consider endocrinology input

• If patient is already on an oral anti-diabetic medication, the dose of ipatasertib should be reduced by one dose level. Otherwise, no dose reduction required.

• If random glucose > 200 mg/dL after 2 weeks of metformin, continue metformin and consider adding sulfonylurea and titrate.

• If random glucose > 200 mg/dL after additional 1 week of metformin and sulfonylurea, consider adding basal insulin. Titrate off insulin when medically appropriate.

Level 3 (≥ 13.9 mM and < 27.8mM; OR ≥ 250 mg/dL and < 500 mg/dL) without symptoms, i.e. polyphagia, polydipsia and polyuria.)	

• Hold* until ≤ Glucose Level 1. Resume at one dose level lower**.

• Immediate endocrinology input and home glucose monitoring, as per treating physician discretion.

• Treat hyperglycemia as medically appropriate.

• Start (or increase) metformin and sulfonylurea and rapidly titrate oral agents.

• If random glucose > 200 mg/dL after additional 1 week of metformin and sulfonylurea, consider adding basal insulin. Titrate off insulin when medically appropriate.

Level 4 (≥ 27.8 mM OR ≥ 500 mg/dL) OR (≥ 13.9 mM and < 27.8mM; OR ≥ 250 mg/dL and < 500 mg/dL with symptoms, i.e.	

• Hold* until ≤ Glucose Level 1. Resume at one dose level lower or discontinue, per investigator discretion** Immediate endocrinology input.

• Treat hyperglycemia as medically appropriate.

• Start (or increase dose of) oral anti-diabetic medications (e.g., metformin).

Glucose Level	Management/Next Dose for Ipatasertib

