polyphagia, polydipsia and polyuria.)	
 
Consider intravenous fluids and/or admit if hypovolemic signs/symptoms.
 
Consider appropriate clinical management of hyperglycemia per local guidelines (insulin infusion etc.).
 
If Glucose Level 4 hyperglycemia recurs, permanently discontinue ipatasertib.
 

*	Patients requiring a delay of > 4 weeks will go off protocol therapy.
**	Patients requiring > two dose reductions will go off protocol therapy.

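### At Glucose Level 3, the Section 3.4 text and the Table 6 row give different insulin instructions, and nothing says which governs

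*Protocol*

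**What the plan says.** The hyperglycemia text in Section 3.4, ahead of Table 6, gives this advice on insulin: "For Glucose Level 3 or 4 hyperglycemia, when insulin therapy is considered, an insulin infusion is recommended. Avoid use of long acting insulin". The sentence continues: "avoid large boluses of short acting insulin, and observe closely for rebound hypoglycemia".

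Table 6 then sets out management by glucose level.

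- **Level 2 row.** Metformin comes first. The next step is conditional on random glucose above 200 "mg/dL after 2 weeks of metformin, continue metformin and consider adding sulfonylurea and titrate". If glucose is still above 200 mg/dL "after additional 1 week of metformin and sulfonylurea, consider adding basal insulin. Titrate off insulin when medically appropriate".
- **Level 3 row.** The range is 13.9 to below 27.8 mM, "OR ≥ 250 mg/dL and < 500 mg/dL) without symptoms". The oral-agent step is "Start (or increase) metformin and sulfonylurea and rapidly titrate oral agents". The insulin step repeats the Level 2 sentence word for word, including the reference to an additional week. No infusion is mentioned.
- **Level 4 row.** "Consider appropriate clinical management of hyperglycemia per local guidelines (insulin infusion etc". Basal insulin is not mentioned.

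At Level 3 ipatasertib is held until glucose returns to Level 1, and under the table's footnote a delay of more than 4 weeks ends protocol therapy.

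Section 2.1.7 lists among the exclusions for patients with diabetes: "Insulin required for routine diabetic management and control".

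**The concern.** The text names Level 3 explicitly and points to an infusion and away from long-acting insulin. The Level 3 row offers basal insulin and nothing else by way of insulin. A site working from the text and a site working from the table could manage the same patient differently, and each could show that it followed the protocol.

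What is at stake is patient safety and consistency between sites. The protocol attaches its own warning of rebound hypoglycemia to the advice against long-acting insulin. Patients with diabetes who need insulin for routine control are excluded at entry, so insulin given at Level 3 would generally be a new start under these instructions.

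**Working it through.** The protocol states no figure to reproduce here. The check compares the two instructions and the glucose ranges in which each applies.

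**1. The instructions side by side**

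| Glucose level | Text in Section 3.4 | Table 6 row |
|---|---|---|
| 2 | Infusion sentence does not cover it | Consider basal insulin |
| 3 | Infusion recommended; avoid long-acting insulin | Consider basal insulin; no infusion named |
| 4 | Infusion recommended; avoid long-acting insulin | Infusion named; no basal insulin |

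Within Levels 3 and 4, which the text covers, the Level 4 row agrees with it and only the Level 3 row departs from it.

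**2. Where both apply**

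Table 6 gives each limit in both units, so its own conversion factor can be recovered:

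- 160 / 8.9 = 17.98
- 250 / 13.9 = 17.99
- 500 / 27.8 = 17.99

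The factor is about 18 mg/dL per mM. The row's basal-insulin trigger of 200 mg/dL is 200 / 18 = 11.1 mM, which lies in Level 2 (8.9 to below 13.9 mM).

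- Above 200 and below 250 mg/dL, the current reading is Level 2 and the text's infusion sentence does not clearly apply.
- From 250 to below 500 mg/dL without symptoms, the reading is Level 3 and also exceeds the 200 mg/dL trigger. Both instructions apply.

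**3. Is there a rule of precedence?**

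The text calls its guidance general, but that remark concerns baseline values and time since food when reading glucose results. It also allows other thresholds, which does not touch the type of insulin. The row asks for endocrinology input and medically appropriate treatment. None of these ranks the text against the table or assigns one to acute and the other to persistent hyperglycemia.

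**4. Timing of the Level 3 step**

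At Level 2, the additional week follows a stated 2 weeks of metformin. The Level 3 row starts or increases both oral agents together and states no earlier period, so the additional week has nothing to follow. Read as one week, the insulin step comes at about week 1. Read as the Level 2 sequence, it comes at 2 + 1 = 3 weeks. Both fall inside the 4-week limit on holding ipatasertib, but they leave 3 weeks and 1 week of it respectively.

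**5. Level 1/Level 2 boundary (minor)**

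In mg/dL, Level 1 is below 160 and Level 2 is above 160, so exactly 160 has no level. In mM the limits meet at 8.9, and 160 / 18 = 8.89 mM falls in Level 1. The gap exists on the mg/dL scale only.

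**The case against.** The strongest reply is that both statements are soft and leave room for specialist judgement. On this view they can be read in sequence: the text covers insulin considered at presentation, and the row covers persistence after a week of oral agents. The order of steps in the row makes that reading plausible. It is not written down, however. The text applies whenever insulin is considered at Level 3 or 4, and a patient still at Level 3 after the oral-agent week is within that wording.

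A second reply is that the protocol never defines basal insulin as long-acting. That is correct, and treating it as ordinarily longer-acting is an assumption. The conflict does not depend on it alone: the text recommends an infusion, while the row offers only basal insulin.

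Third, the situation is narrow, and the patient's ipatasertib should be on hold at that point. This stands and limits the size of the problem. It does not tell a site which instruction to follow.

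Fourth, the additional-week and 160 mg/dL points are secondary. One week on the two oral agents is a natural reading at Level 3, and the mM limits do assign 160 mg/dL to a level. Both are wording faults worth correcting in the same edit and would not justify the finding by themselves.

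**Conclusion.** The concern holds and should be fixed. For an asymptomatic patient whose glucose stays at 250 to below 500 mg/dL (13.9 to below 27.8 mM) after the oral-agent week, Section 3.4 gives two insulin recommendations that point in different directions and does not say which governs.

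The protocol gives no frequency for this situation. Table 6 uses glucose levels and not CTCAE grades, so the single grade 3 hyperglycemia among 51 patients in the cited single-agent study cannot be converted into an expected count. No patient number is claimed, and there is no effect on sample size or analysis.

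The conclusion rests on two readings. Basal insulin is taken as ordinarily longer-acting, which strengthens the conflict but is not essential to it. The advice against long-acting insulin is taken to share the Level 3 or 4 scope of the sentence before it. That second sentence names no level itself; if it were read without restriction, the identical basal-insulin step in the Level 2 row would conflict with it too.

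**What to change.** The sponsor's clinical team should reconcile the insulin advice in the Section 3.4 hyperglycemia text with the Level 3 row of Table 6, so that a site finds one instruction at that level. The reconciled wording should make clear which glucose levels the advice on long-acting insulin covers. The row should also state what period its additional week follows. Which clinical rule applies is for that team to decide, and this review takes no position on it.

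In the same edit, the Level 1 and Level 2 limits in mg/dL should be made contiguous, as they already are in mM.

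The cost is wording in one block of text and one table. No procedure, visit or data item is added.
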